7. BACKGROUND AND SIGNIFICANCE

Essential Tremor (ET) is the most common tremor disorder, currently affecting an estimated 2.9 million Americans and leading to disability and decreased quality of life in 75% of cases. Individuals with ET commonly experience tremors involving the arms that manifest during movement (kinetic tremors) or during sustained anti-gravity postures (postural tremors). This has a direct impact on the individual's ability to function in the workplace and/or perform their activities of daily living (e.g. eating, bathing). Diagnosis of ET is

commonly made based on consensus clinical criteria, and a history of alcohol- responsive tremors is highly suggestive of ET. Clinical management for moderate to severe cases begins with selection of a pharmacological agent with at least modest efficacy and favorable side effect profile, based on published treatment practice guidelines. Categories of centrally-active agents shown to have at least modest efficacy on ET include beta-blockers (e.g. propranolol), antiepileptics (e.g. primidone, topiramate), and benzodiazepines (e.g. clonazepam). Despite the seeming diversity of agents for ET, 25-55% of patients gain no benefit and side effects are common and may limit long-term use. Furthermore, there appears to be a dissociation of tremor subtypes, with some patients showing greater improvement in one subtype of tremor than the other, though this has not been rigorously studied. The proposed work seeks to address many of these current barriers to progress in ET research including: 1) limited knowledge of the brain regions generating ET; 2) unknown and possibly independent mechanisms for postural and kinetic tremors; and 3) unknown mechanism of action of various agents on the tremor network(s). Using a non-invasive method like fMRI to study the whole brain, we aim to further characterize the ET neural network(s), determine whether postural and kinetic tremors are associated with different neural networks, and elucidate the mechanism of action of two pharmacological agents on the ET neural network(s). Knowledge gained from this study will have a direct impact on the development of targeted agents with less systemic adverse effects and will provide additional knowledge about the phenotypic variability of ET. Ultimately, this will potentially lead to more patient-specific treatment algorithms and will improve quality of life for patients with ET.

8. PROGRESS REPORT

- 1. Our recruitment efforts have been maintained during the past year. In addition to enrollment from [name] clinic, we are receiving numerous inquiries from potential participants who find this project listed on the International Essential Tremor Foundation (IETF), Tremor Action Network, and HopeNET websites. In addition, the IETF organized a number of ET information events across the country. [name] and/or the study coordinator attended meetings in Boca Raton, Miami, and Tampa, Florida with study-related materials and information to minimize the complexity of travel to Miami. In addition, a number of individuals have personally flown to Miami to participate from Nevada, Georgia, and even South America. To date, we enrolled 22 subjects with Essential tremor and 8 matched controls for a total of 30 subjects from the University of Miami, 27 of which have completed their participation. Three subjects did not complete the study. One ET subject withdrew prior to MRI due to a new serious medical condition that took precedence over participating in study. Another ET subject was "lost to follow-up" and the third control subject did not complete due to experiencing claustrophobia just prior to starting MRI. We have no adverse events to report and no subject receiving alcohol experienced intoxication based on both clinical assessment and the use of the standardized Alcohol Intoxication Scale. Of those subjects who were enrolled on tremor medications, all were able to safely taper off of their medications with an expected worsening of their tremors. Since we plan to collect up to 55 ET subjects and 33 matched controls over the life of the grant, we continue to allow for a slight lag in the collection of the controls to ensure we collect subjects well---matched to our ET subject group and since the recruitment of controls is likely to be a simpler process.
- 2. Recruitment efforts for the upcoming year in San Diego will maintain collaborations with the various national and international tremor foundations. In addition, subjects will be enrolled from the UCSD Movement Disorders Center and the surrounding community. We continue to anticipate no problems in recruiting the sample size proposed.

9. RESEARCH DESIGN AND METHODS

The study population will include patients diagnosed with essential tremor (ET) and healthy volunteers without a major neurological disorder based on inclusion/exclusion criteria described in section 10. All subjects will be recruited nationally with the aid of ET foundations and support groups, locally, and from the movement disorder clinic at UCSD. Every potential subject expressing interest in participating will undergo a telephone pre-screening to ensure they fulfill inclusion-exclusion criteria before being invited for the formal evaluation (screening visit). In order to balance the ethical conflicts of clinician and researcher, all potential participants will be provided with the informed consent form beforehand to review with their loved ones, thus eliminating the pressure to decide immediately whether to participate in study. Informed consent will be discussed with the subject by the study team. The informed consent phase will engage not only the subject but also the family members and/or friends and everyone involved is given the opportunity to ask questions and address concerns. Subjects providing informed consent will then be enrolled into the study.

Healthy Volunteer Study Procedures

SCREENING

After being screened for eligibility and providing informed consent, volunteers will have a thorough

examination that will lasts approximately 2-hours. PI will obtain medical history, and a videotaped neurological exam that includes the following assessments: United Parkinson's Disease Rating Scale (UPDRS), Essential Tremor Rating Assessment (TETRAS), Montreal Cognitive Assessment (MOCA), Scale for the Assessment and Rating of Ataxia (SARA), baseline Spirography and Accelerometry. If PI finds any non-ET abnormalities during the evaluation, the subject will be excluded and advised to consult their personal physician.

VIDEO RECORDING

As part of the evaluation, a video recording will be collected to document exam findings. Participants decide whether these videos may be used solely by the research team for this research project, or additionally may be used for other purposes such as educational or scientific meetings.

BLOOD SPECIMEN COLLECTION

As a part of the screening visit, participants will be asked permission to collect a blood sample that will be used as a control for future genetic research on ET and related disorders. The total amount of blood removed will not exceed 20 ml (4 teaspoons).

FUNCTIONAL MRI (FMRI)

After completion of the screening visit, subjects will be scheduled for the fMRI visit that will last no more than 2-hours. Subjects will be asked to lie still for up to 15 minutes at a time. An accelerometer device will be placed on the hand to measure movement. We will use fMRI to observe the brain's activity during three (3) different activities: arms resting by the side, right arm elevated and maintained in the air, and while drawing a spiral with the right hand. These tasks will be performed multiple times during 5-minute runs.

At the completion of study participation, subjects will receive payment for their participation. Payments for incomplete participation will be prorated based on consent form guidelines.

ET Volunteer Study Procedures

SCREENING

Subjects will be screened for eligibility and after providing informed consent, PI will conduct an examination to confirm the diagnosis of Essential Tremor (ET) and to exclude any other neurologic disorder. PI will obtain medical history, and a videotaped neurological exam that will include the following assessments: United Parkinson's Disease Rating Scale (UPDRS), Essential Tremor Rating Assessment (TETRAS), Montreal Cognitive Assessment (MOCA), Scale for the Assessment and Rating of Ataxia (SARA), baseline Spirography and Accelerometry. A urine pregnancy test will be performed on female participants of childbearing potential.

VIDEO RECORDING

As part of the evaluation, a video recording will be collected to document exam findings. Participants decide whether these videos may be used solely by the research team for this research project, or additionally may be used for other purposes such as educational or scientific meetings.

BLOOD SPECIMEN COLLECTION

As a part of the screening visit, participants will be requested to provide a blood sample that will be used for future genetic research on ET and related disorders. The total amount of blood removed will not exceed 20 ml (4 teaspoons).

MEDICATION TAPER

A tremor medication consultation will be conducted with the PI reviewing the medication history. Participants taking no medications for ET will proceed to be randomized to one of the two fMRI visits (A or B). If a subject is on tremor medications and gives consent to participate in this study, tremor medications will need to be discontinued. This plan may be carried out by either the subject's primary physician or study PI in consultation with the Safety Advisory Committee (see section 14), depending on preference of subject and

treating physician. If subject has a treating physician, the PI will contact the physician to discuss whether there are any potential safety concerns with tapering tremor medications and review the plan to taper/titrate medications; taper will only occur with physician approval. The duration of the medication taper prior to MRI visit A depends on the type of tremor medication the subject is on with the period being at least five half-lives. In terms of the period between MRIs, this may be as short as two weeks and up to several months, though no explicit time limitations are set. The duration depends upon the time needed for a subject to taper off all tremor medications for MRI visit A, and the time necessary to reach a steady state of propranolol SR for MRI visit B. If a subject cannot tolerate the medication taper (e.g. worsening tremors create undo disability or the presence of an unexpected adverse effect), the PI will consult with the Safety Advisory Committee and discuss restarting medications with subject and treating physician (if present) and subject will be withdrawn from the study.

FUNCTIONAL MRI (FMRI) OVERVIEW

After completion of the screening visit, subjects will be scheduled for the fMRI visit that will also last approximately 2-hours. Women of childbearing potential will undergo a second urine pregnancy test prior to MRI visit A. ET participants already on stable doses of Propranolol SR will first undergo fMRI on Propranolol SR. Participants taking no medications for ET will be randomized to one of the two fMRI visits (A or B). After completion of one, participants will undergo the other visit type.

FMRI VISIT A

During this visit, subjects will remain off tremor medications for a set period of time. The PI will provide specific instructions about how to do this since it varies based on the individual subject's medication history. Women of childbearing potential will undergo a second urine pregnancy test prior to MRI. During this visit, subject will be asked to perform three different activities: arms resting by the side, right arm elevated and maintained in the air, and while drawing a spiral with the right hand. Subject will perform these tasks multiple times during 5-minute runs. PI will then provide subject with a single 50-ml serving (1 shot) of 40% ethanol to drink and a high resolution structural MRI is performed, during which time the tremor suppression effects will begin. The same tasks performed during the first half of the study will be repeated. PI will complete an Alcohol intoxication Scale at the onset of the visit and again after MRI to ensure subjects are not intoxicated upon discharge. Subjects who demonstrate signs of intoxication will be monitored until they are back to their baselines.

FMRI VISIT B

During this visit, we will study how the brain and tremors respond to propranolol SR (Inderal LA). Before participating in this visit, subjects will need to be on a stable dose of this medication. In order to accomplish this, the subject will receive detailed instructions from PI on how to start and increase the medicine in consultation with the treating physician and/or Safety Advisory Committee. Subject responses to medication (benefits and adverse effects) will be monitored through weekly telephone calls. Once a stable dose of medication has been achieved, the subject will be scheduled for the fMRI scan. During this visit, the subject will be asked to perform three different activities: arms resting by the side, right arm elevated and maintained in the air, and while drawing a spiral with the right hand. At the completion of the visit, the study investigator will instruct the subject on how to taper off this medicine based on consultation with the treating physician and/or Safety Advisory Committee.

STUDY COMPLETION

Three (3) scenarios exist for study completion/termination:

1) Premature termination prior to completion of all visits

In this scenario, the subject will return to their baseline medications under the direction of their treating

physician and/or PI in consultation with the Safety Advisory Committee. Payments for incomplete participation will be prorated based on consent form guidelines.

- 2) Subject who was not initially on tremor medications completes the study. PI will discuss with the subject whether they wish to return to being on no medications or whether they wish to remain on propranolol SR. If no medications are requested, PI will guide/assist with tapering schedule in consultation with the treating physician and/or Safety Advisory Committee. If subject wishes to stay on propranolol SR, PI will assist or coordinate with primary treating physician to keep subject on the medication after the completion of the study at the subject's expense. Subject will receive payment for study completion.
- 3) Subjects who were on tremor medication(s) at start of the study. The PI will confirm with subject their desire to restart their tremor medications. PI will guide/assist with titration schedule in consultation with the treating physician and/or Safety Advisory Committee. Subject will receive payment for study completion.

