10. HUMAN SUBJECTS

Population:

88 volunteers (Age 21 or over) will participate in this study. This includes a total of 55 ET subjects and 33 matched controls. Of these, 27 subjects have already completed participation and were enrolled at the University of Miami. Thus, 61 additional subjects will be enrolled at UCSD. Participants will be selected without regard to ethnicity or race.

Inclusion Criteria ET Patients:

- Age 21 or over
- Subjects willing to abstain from caffeine or alcohol for 48 hours prior to the fMRI scanning
- Diagnosis of Essential Tremor by a Movement Disorder specialist based on Tremor Research Group criteria

Age-matched Controls:

- Age 21 or over
- Absence of a primary neurological diagnosis

Exclusion criteria All Subjects:

- Abnormal findings on neurological exam consistent with an organic disorder
- Presence of a resting tremor on exam
- Pregnant, nursing, or suspected pregnancy
- Finding on the MRI safety questionnaire contraindicating MRI
- History of dementia, brain tumor, stroke, head trauma or a vascular malformation as obtained by history or from imaging studies
- History of a severe medical condition, such as cardiovascular disease, preventing subject from lying flat for up to 120 minutes
- Lacking the capacity to provide informed consent
- Claustrophobia or other restrictions that prevent subject from undergoing a scan in a confined space for up to 120 minutes
- Acute or chronic medications that influence hepatic metabolism or CNS function and cannot be temporarily discontinued for the length of the study
- Use of beta blocker medications for the management of hypertension

ET Patients:

- Movement frequency and severity preventing safe and effective MRI data collection
- Active or prior history of alcohol abuse or dependence
- Subject unwillingness to take a potentially intoxicating drug (ethanol)

- You do not have an accompanying adult who can provide transportation for you after consuming alcohol during one of the MRI visits
- You have an allergy to alcohol (ethanol)
- History of deep brain stimulation surgery or thalamotomy

Age-matched Controls:

• Use of a medication known to have tremor effects that cannot be temporarily tapered and discontinued (see below).

List of Medications with Known Tremor Activity:

Benzodiazepines (any)

Beta-blockers (any)

Carbemazepine

Gapapentin

Levetiracetam

Oxybate

Phenytoin

Primidone

Topiramate

Valproic acid

Zonisamide

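### No urine pregnancy test is listed before the Visit B MRI, although ET women of childbearing potential are tested at screening and before the Visit A MRI

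*Combined protocol and SAP*

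**What the plan says.** Section 10 lists "Pregnant, nursing, or suspected pregnancy" among the exclusions for all subjects. Section 14, under the risk of MRI, also says that pregnant women will not take part.

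For ET participants, Section 9 provides for testing as follows:

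- **Screening:** "A urine pregnancy test will be performed on female participants of childbearing potential".
- **fMRI overview:** "Women of childbearing potential will undergo a second urine pregnancy test prior to MRI visit A".
- **fMRI Visit A:** "Women of childbearing potential will undergo a second urine pregnancy test prior to MRI". This is the same second test stated again, not a third one.
- **fMRI Visit B:** no test. The text covers starting and increasing propranolol SR, telephone follow-up, the scan and the taper. On timing it says "Once a stable dose of medication has been achieved, the subject will be scheduled for the fMRI scan".

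On the period between the two MRIs, the medication taper text in Section 9 says "this may be as short as two weeks and up to several months, though no explicit time limitations are set". On order, participants on no ET medication are randomized to A or B first, while "ET participants already on stable doses of Propranolol SR will first undergo fMRI on Propranolol SR".

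**The concern.** The protocol rules out pregnancy for the whole study and gives the rule again as an MRI precaution, yet it attaches the repeat test to only one of the two ET MRI visits. A pregnancy that began after the last listed test would not be picked up by any listed test before the Visit B scan. At that scan the woman is taking propranolol SR, in many cases started on the study's instructions.

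What is at stake is participant safety and keeping to the protocol's own exclusion. Randomization, endpoints, power and error rates are not involved.

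**Working it through.** The plan states no figure to reproduce. The check has two parts: placing the listed tests against the visit order, and sizing the group.

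**1. Listed tests by visit order (Section 9)**

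| Order | Who | Last listed test before the Visit B scan | Age of that test at Visit B |
|---|---|---|---|
| A then B | Includes those on no ET medication who are randomized to A first | Visit A test | Two weeks to several months, no explicit limit |
| B then A | Those on no ET medication who are randomized to B first; those already on stable propranolol SR | Screening test | Not stated |

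Listed tests per ET woman of childbearing potential: screening 1, Visit A 1, Visit B 0. In the B-then-A order, the second test takes place after Visit B is over.

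**2. Remaining ET subjects**

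Section 8 reports 22 ET subjects and 8 controls enrolled, with 2 ET subjects and 1 control not completing.

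- Completed: 22 − 2 = 20 ET and 8 − 1 = 7 controls; 20 + 7 = 27, as Section 8 states.
- Remaining: 55 − 20 = 35 ET and 33 − 7 = 26 controls; 35 + 26 = 61, as Section 10 states.

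Each remaining ET subject has one Visit B, so at most 35 Visit B scans remain.

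**3. Women of childbearing potential**

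The protocol does not give this share. Section 6 notes that ET becomes more common after age 40, which suggests a small one. I assume 5% to 20%.

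- Visit B scans affected: 0.05 × 35 = 1.75 and 0.20 × 35 = 7.0, so about 2 to 7.

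**4. Those who would start propranolol in the study**

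Section 19 says at least 30% of ET subjects already take propranolol SR or its brand-name equivalent. Taking 30% for the remaining 35:

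- Starting in the study: 0.70 × 35 = 24.5.
- Women of childbearing potential among them: 0.05 × 24.5 = 1.2 and 0.20 × 24.5 = 4.9, so about 1 to 5.

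Because the 30% is a minimum, a higher true share would lower these last counts.

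**The case against.** The strongest reply is that the placement may be deliberate and that other safeguards cover Visit B.

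- **Ethanol.** Visit A is where the study gives 50 ml of 40% ethanol, which would be a sensible reason for a repeat test there. This may be part of the reason. But Section 9 ties the test to the MRI, and Section 14 states the bar on pregnancy under MRI risk. Both apply equally to Visit B.
- **Self-report and withdrawal.** Section 10 closes by saying that eligibility rests on self-report, and Sections 14 and 15 let the investigator withdraw a subject for safety. A reader might infer from the missing test that the exclusion goes unchecked at Visit B. The documents do not support that; they show only that no urine test is listed. Still, a woman cannot report a pregnancy she does not know about.
- **Test-day MRI screening.** Section 15 repeats MRI safety screening at the start of the test day and right before scanning. The questionnaire is not in the documents, so whether it asks about pregnancy cannot be seen. No test is named.
- **Telephone follow-up.** "Subject responses to medication (benefits and adverse effects) will be monitored through weekly telephone calls". Pregnancy is not mentioned there.
- **Timing.** A test just before the Visit B scan comes after titration, so it cannot prevent earlier exposure. This stands. Such a test confirms the exclusion before the scan and could shorten further exposure, since Section 9 lets some subjects stay on the drug afterwards. A test close to the first dose would do more about exposure.
- **Size of harm.** The propranolol risk lists in Sections 14 and 15 name no pregnancy risk, and the protocol describes MRI as low risk. The documents therefore do not allow the harm to be quantified.

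**Conclusion.** The gap is real but small: no urine pregnancy test is listed before the Visit B MRI, in either visit order. It concerns about 2 to 7 of at most 35 remaining Visit B scans. About 1 to 5 of these would be in women who start propranolol in the study. Both ranges rest on the assumed 5% to 20% share, and the second also on 30% already taking the drug. The missing listing is certain; how far the unseen MRI questionnaire closes the gap is not.

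Four stronger readings should be resisted:

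- A reader might infer that women start study propranolol untested. The screening test precedes any in-study start.
- A reader might infer that Visit B always follows an in-study titration, or that the open-ended interval applies to Visit B itself. Those already on stable propranolol SR go to Visit B first, and the wording about time limits concerns the period between the two MRIs.
- A reader might extend the point to controls, whose procedures list no test. Controls receive no study drug and have one scan that the protocol regards as low risk, so the point is not made for them.
- A reader might look for an effect on the results. There is none on randomization, endpoints or analysis.

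This is an improvement to consider, not a flaw that undermines the study.

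**What to change.** In Section 9, fMRI overview, replace the sentence on the Visit A test with wording such as: *Each ET participant of childbearing potential has a urine pregnancy test before MRI Visit A and again before MRI Visit B.* Put a matching line under fMRI Visit B. Under fMRI Visit A, delete the word for second, because in the B-then-A order that test would become the third.

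Where propranolol SR is started in the study, preferably also test shortly before the first dose. The documents give no basis for a particular number of days, so the study team should set the window.

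Cost: protocol wording plus one extra urine test per ET woman of childbearing potential, about 2 to 7 in all. With the first-dose test the total is about 3 to 12 (1.75 + 1.2 = 2.95 and 7.0 + 4.9 = 11.9), under the same assumptions. The study already uses this test, and the statistical analysis does not change.
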